#### 8. SAFETY EVALUATION

Safety evaluation results form part of the primary and secondary objectives of this study.

#### **8.1** Adverse Events

The following information is to be obtained from the eCRF:

• AEs (*Adverse Events* eCRF panels).

- Date and time of BAX 855 administration (*Study Infusions* eCRF panels).
- Reason for not completing the study (*Study Completion/Termination* eCRF panels).

Adverse events are to be coded using the Medical Dictionary for regulatory activities (MedDRA) as documented in the Data Management documentation at the time of performing the analysis.

The following derivations based on eCRF reported results are to be performed:

- AEs are considered to have occurred during or after BAX 855 administration if:
  - The known start date and/or time of the AE is equal to or after the date and/or time of first BAX 855 administration in the current study.
  - The eCRF question "When did event occur in relation to treatment with BAX 855?" has a response of any of the following:
    - During treatment.
    - Within 24 hours after last treatment.
    - After more than 24 hours from last treatment.
- Time since last BAX 855 infusion is to be determined as:

Time = [Start Date/Time of AE] - [Date/Time of Last BAX 855 Exposure] where the date/time of last BAX 855 exposure are the last possible BAX 855 administration, regardless of reason, prior to the start of the AE. Time since last BAX 855 infusion is only to be determined if the full start date (regardless of whether time is known or not) of the AE is known. Time since last BAX 855 infusion is to be presented in either hours or days, based on the following criteria:

- Presented in hours if start time of AE is known and time since last BAX 855 infusion is < 24 hours.
- Presented in days if start time of AE is known and time since last BAX 855 infusion is  $\geq$  24 hours.
- o Presented in days if start time of AE is not known.
- Duration of AE is to be determined as:

 $Duration = [End \ Date/Time \ of \ AE] - [Start \ Date/Time \ of \ AE]$  The duration of an AE is to be presented in either hours or days, based on the following criteria:

- Presented in hours if both start time and end time of the AE is known and the duration is < 24 hours.
- Presented in days if both start time and end time of the AE is known and the duration is  $\geq$  24 hours.

- o Presented in days if either start time or end time or both are unknown.
- An AE is considered non-serious if the eCRF question "Was AE serious?" is answered "No" and considered serious if the question is answered "Yes".
- An AE is considered severe if the eCRF question "Severity" is answered "Severe".
- An AE is considered related as assessed by the Investigator if the AE is indicated as "Possibly related" or "Probably related" in the eCRF. An AE is considered unrelated as assessed by the Investigator if the AE is indicated as "Not related" or "Unlikely related" in the eCRF.
- An AE is considered related as assessed by the Sponsor if the Sponsor Medic deem the AE related to the study medication. Prior to any analyses described in this SAP, a list of all AEs in the database is to be provided to the Sponsor Medic to assess relationship from a Sponsor perspective of AE to study medication.
- An AE is considered leading to discontinuation of study medication if indicated as "Drug withdrawn" in the eCRF.
- An AE is considered leading to discontinuation of study if the AE is indicated as the primary reason why the subject did not complete the study from the *Study Completion/Termination* eCRF panel.
- An AE is considered as leading to death if the question "Did the serious event result in death" is indicated as "Yes" or if the outcome in the eCRF is indicated as "Fatal".
- An AE is considered to be an allergic reaction if the question "Was this event considered to be an allergic reaction" is indicated as "Yes".
- An AE is considered to be a thrombotic event if the question "Is this a thrombotic event" is indicated as "Yes" in the eCRF.

AEs that occurred during or after BAX 855 are to be presented for the SAS. Summary tables are to indicate the number of subjects who experienced AEs as well as the number of AEs. Summaries for BAX 855 as indicated in the latest version of the Output Templates are also to include the rate of AEs per 100 infusions and rate of AEs per year. In addition, tables are to be prepared to summarize each AE by system organ class and preferred term, the number of subjects who experienced an AE at least once, the rate of subjects with AE(s), AEs per 100 infusions and AE rate per year. AE summaries by seriousness, severity and relationship are to be presented as well.

AE rate per 100 infusions is to be determined as the number of AEs divided by the total number of infusions (regardless of the reason the infusion was administered) in the study multiplied by 100.

AE rate per year is to be determined as the number of AEs divided by the OPE in years in the current study across all subjects.

All AEs for each subject, are to be listed for the SAS.

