12.1.2 Assessment of Adverse Events

Each AE from the first IP exposure until study completion/discontinuation will be described on the AE eCRF using the medical diagnosis (preferred), or, if no diagnosis could be established at the time of reporting the AE, a symptom or sign, in standard medical terminology in order to avoid the use of vague, ambiguous, or colloquial expressions (see definition in Section 12.1). Each AE will be evaluated by the investigator for:

- Seriousness as defined in Section 12.1.1.1
- Severity as defined in Section 12.1.2.1
- Causal relationship to IP exposure or study procedure as defined in Section 12.1.2.2

For each AE, the outcome (ie, recovering/resolving, recovered/resolved, recovered/resolved with sequelae, not recovered/not resolved, fatal, unknown) and if applicable action taken (ie, dose increased, dose not changed, dose reduced, drug interrupted, drug withdrawn, not applicable, or unknown) will also be recorded on the AE eCRF. Recovering/resolving AEs will be followed until resolution, medically stabilized, or 30 days after the study completion/termination visit, whichever comes first). If the severity rating for an ongoing AE changes before the event resolves, the original AE

report will be revised (ie, the event will not be reported as separate AE). During the course of any AE, the highest severity rating will be reported.

Deviations from the protocol-specified dosage (including overdosing, underdosing, abuse, and withdrawal, treatment errors (including incorrect route of administration, use of an incorrect product, and deviations from the protocol-defined dosing schedule), failures of expected pharmacological actions, and unexpected therapeutic or clinical benefits will be followed with regard to occurrence of AEs, lack of efficacy, and/or other observations because these events may be reportable to regulatory authorities.

Any pregnancy that occurs after administration of IP will be reported on a Pregnancy Form and followed-up at 1 year post-delivery, if feasible.

If an investigator becomes aware of an SAE occurring in a subject after study completion, the SAE must be reported on the SAE Form within 24 hours after awareness; no additional reporting on eCRFs is necessary.

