20.2.2.3 Baseline Visit / Start of Prophylaxis

This visit takes place 6 ± 1 weeks following the PK assessment, or following screening if a PK was already available in case of transitioning subjects. This visit will then coincide with confirmation of eligibility. It is the baseline time point for all subsequent visits.

At least 84 to preferably 96 hours must have elapsed since the previous BAX 855 administration and at least 72 hours since the previous administration of any other FVIII concentrate in case of BAX855 naïve subjects, and the subject must not be actively bleeding.

The following procedures will be performed:

Pre-infusion:

- Confirmation of eligibility for transitioning subjects with previous PK data
- Physical examination, including height (for subjects aged < 18 years at enrollment) and body weight
- Review and discuss subject e-diary, including:
 - Review bleeding episodes and their treatment (not applicable for BAX855 naïve subjects)
 - Adverse events
 - Concomitant medications and non-drug therapies
- Laboratory assessments within 30 minutes of start of infusion:
 - FVIII activity and antigen
 - TGA parameters and VWF antigen (optional in subjects aged <12 years)
 - Immunogenicity tests
 - Hematology, clinical chemistry, and lipid panel
- PROs:
 - Bleed and pain severity using Haemo-SYM (≥ 18 years), HRQoL using SF-36 (≥ 14 years), HRQoL using PedsQL (< 14 years), patient satisfaction with treatment using the Satisfaction Questionnaire (all ages), and Patient Activity Level (all ages)
- Vital signs (within 15 minutes of start of infusion)

Determination of IR:

- Infusion of 60 ± 5 IU/kg BAX 855

Post-infusion:

At 30 ± 15 min post-infusion:

- FVIII activity and antigen
- TGA parameters (optional in subjects aged < 12 years)
- Vital signs

Other procedures:

- Dispense IP:
 - A sufficient quantity of IP will be dispensed to cover the period until the next scheduled visit in 4 ± 1 week.

20.2.2.4 Follow-up Visits: At 4 (\pm 1) Weeks, 8 (\pm 1) Weeks, 18 (\pm 2) Weeks from Baseline Visit

No wash-out period is required for this visit and the patient should not be in a bleeding state.

The visit should be performed immediately prior to the next regular prophylactic infusion in order to determine adequate FVIII trough levels.

The following assessments will be performed:

Pre-infusion:

- Physical examination, including height (for subjects aged < 18 years at enrollment) and body weight
- Review and discuss subject e-diary, including:

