## 6.7 Extent of Exposure

The following information is to be obtained from the eCRF:

- Information on study infusions (*Study Infusions* eCRF panels).
- Treatment regimen, including planned dose (*Treatment Assignment* and *Change of Treatment Assignment* eCRF panels).
- Body weight (*Vital Signs* eCRF panels).

The following derivations based on eCRF reported results are to be performed:

- Body weight-adjusted dose (IU/kg) is to be derived as the total units infused (IU) divided by the last available body weight (kg) prior to the infusion. Refer to Section 5.4: Handling of Missing, Unused, and Spurious Data for imputation schemes to be implemented.
- Total number of infusions in this study are determined as the count of the number of infusions, regardless of date and time, the subject had. Number of infusions are to be determined overall and by reason for infusion as well as by the treatment regimen assigned to at the time of receiving the treatment.
- The number of EDs are determined as the number of unique calendar days on which a subject received any or part of any infusion. Multiple infusions on the same day are still to be considered one ED. EDs are to be determined overall as well as for each reason an infusion is given. The number of EDs will be determined for this study and across all previous BAX 855 studies the subject participated in. EDs in this study will be derived as the number of infusions on unique calendar days in this study, while EDs from previous BAX 855 studies will be obtained as reported in the eCRF. The total EDs across all BAX 855 studies will be determined as the sum of EDs in current study and EDs in previous studies.
- The observation period for efficacy (OPE) in days in the study for subjects who never transferred to the surgery study is to be determined as:

$$OPE(Days) = (Stop\ Date - Start\ Date) + 1$$
 where "Start Date" refer to the first BAX 855 infusion in the current study and "Stop Date" to the last BAX 855 infusion in the current study. For subjects on the PK-guided regimen, first BAX 855 infusion will be the first prophylactic infusion.

• The OPE in days for subjects that did transfer to the surgery study is to be determined as:

$$OPE(Days)$$

$$= (Date\ of\ Transfer\ to\ Surgery\ Study - Start\ Date) + (Stop\ Date - Return\ Date\ to\ Current\ Study) + 1$$
where "Start\ Date" and "Stop\ Date" are\ defined\ as\ above.

• The OPE in weeks is to be determined from the OPE in days as:

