$$OPE(Weeks) = \frac{OPE(Days)}{365.2425} \times 52$$

• The OPE in months is to be determined from the OPE in days as:

$$OPE(Months) = \frac{OPE(Days)}{365.2425} \times 12$$

• The OPE in years is to be determined from the OPE in days as:

$$OPE(Years) = \frac{OPE(Days)}{365.2425}$$

- All OPE calculations to be performed overall and per treatment regimen.
- The average number of infusions per time period (weeks, months, years) is to be determined as the total number of infusions during the observation period divided by the duration for the particular time period (weeks, months, years).
- Total dose (IU/kg or IU as applicable) is to be determined as the sum of all doses, overall and by reasons for infusion, during the observation period in the current study.
- The average dose per time period (weeks, months, years) is to be determined as the total dose (IU/kg or IU as applicable) the subject received during the observation period in the current study, divided by the duration for the particular time period (weeks, months, years).
- Average dose per bleed is determined as the sum of all doses (IU/kg or IU as applicable) given to treat bleeding episodes divided by the number of bleeds observed for the particular subject in the current study.

Extent of exposure is to be summarized using descriptive statistics for the SAS, and PPAS and listed for the SAS. Summaries are to be presented by age category and treatment regimen at time of dose.

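### The AE rate per year counts AEs from the first BAX 855 infusion but divides by an efficacy period that, for BAX 855 naive PK-tailored subjects, starts 5 to 7 weeks later

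*SAP*

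**What the plan says.** **Numerator.** Under SAP 8.1, an AE counts as during or after treatment if its start "is equal to or after the date and/or time of first BAX 855 administration in the current study". Events more than 24 hours after the last infusion are also accepted. Protocol 12.1.2 sets the collection window: "Each AE from the first IP exposure until study completion/discontinuation will be described on the AE eCRF". SAP 4.2 lists the PK-assessment infusion among the records that count as BAX 855 dosing, so a PK infusion opens the count.

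**Denominator.** SAP 8.1 states: "AE rate per year is to be determined as the number of AEs divided by the OPE in years in the current study", and goes on to pool over all subjects. SAP 6.7 lets the OPE start date "refer to the first BAX 855 infusion in the current study" and ends OPE at the last such infusion. It then makes an exception: "For subjects on the PK-guided regimen, first BAX 855 infusion will be the first prophylactic infusion". The same section adds: "All OPE calculations to be performed overall and per treatment regimen". I read PK-guided there as the regimen called PK-tailored elsewhere.

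**Timing.** Protocol 20.2.2.3, on the visit at which PK-tailored prophylaxis starts, says: "This visit takes place 6 ± 1 weeks following the PK assessment", or the same interval after screening if PK data already exist. Protocol 10.3.2 keeps naive subjects on their own FVIII product until then, apart from the single BAX 855 infusion for PK.

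**The concern.** A rate per year is interpretable only if events and person-time cover the same window. Here the count opens at the PK infusion, while the clock for a naive PK-tailored subject opens at the start of prophylaxis. The error at the start date can only push the rate up.

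The uncounted weeks follow first exposure to a PEGylated product, and Protocol 6.5 names hypersensitivity as a possible reaction. A naive subject who stops after the PK infusion remains in the safety analysis set and can add AEs, but has no prophylactic infusion from which an OPE could start.

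The late start may suit a bleeding rate under prophylaxis. It sits oddly with the rest of the safety plan: SAP 5.3 sets Day 1 at the first BAX 855 infusion in this study, and the companion rate per 100 infusions counts infusions given for any reason. The SAP defines no separate period for safety. Because AE rates are planned by system organ class and preferred term, one definition feeds many tables.

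**Working it through.** The documents state no AE rate, person-time or share of PK-tailored subjects, so there is no planned figure to reproduce. The sizing below follows from the definitions.

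**Inputs**
- Gap for naive PK-tailored subjects: 6 ± 1 weeks, that is 5 to 7 weeks (Protocol 20.2.2.3).
- OPE: a naive subject starts with no earlier BAX 855 exposure days and needs at least 100 (Protocol 8.3). At twice weekly, 100 / 2 = 50 weeks.
- Assumptions: a constant AE rate; for the pooled figure, equal OPE in all subjects and a share f of subjects affected.

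**One subject.** With true rate λ, expected AEs are λ × (OPE + gap), and the SAP divides by OPE. The ratio of reported to matched rate is (OPE + gap) / OPE = 1 + gap / OPE.

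| OPE | gap 5 wk | gap 6 wk | gap 7 wk |
|---|---|---|---|
| 25 weeks | +20% | +24% | +28% |
| 50 weeks | +10% | +12% | +14% |
| 1 year (52.18 weeks) | +9.6% | +11.5% | +13.4% |

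Example: a matched rate of 2.00 AEs per year is reported as 2.00 × 56 / 50 = 2.24 with a 6-week gap and 50 weeks of OPE.

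The 25-week row needs 100 / 25 = 4 exposure days a week, or early discontinuation. In the other direction, Protocol 8.3 allows follow-up beyond 100 exposure days: a 6-week gap is 6 / 104.4 = about 6% at 2 years and 6 / 156.5 = about 4% at 3 years.

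**Pooled rate.** Total AEs are λN(OPE + f × gap) and total OPE is N × OPE, so the overstatement is f × gap / OPE. With a 6-week gap and 50 weeks of OPE this is 0.12 × f:

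| share affected (assumed) | 5% | 10% | 30% | 50% |
|---|---|---|---|---|
| overstatement | 0.6% | 1.2% | 3.6% | 6.0% |

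**Transitioning PK-tailored subjects.** Protocol 20.2.2.1.1 uses the term first prophylactic infusion for the fixed-dose infusion at screening.
- If SAP 6.7 means that infusion, the gap is nil, or days if an incremental recovery infusion came first.
- If it means the first PK-tailored dose, the gap is 5 to 7 weeks with PK data already available. Without them, it is up to 45 / 7 + 7 = 13.4 weeks, since the PK assessment may fall up to 45 days after screening.

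The SAP does not say which, nor how the overall OPE starts for a subject who switches regimen.

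**The case against.** **Scope.** A reader might infer that every PK-guided subject is affected. The documents do not support that. Transitioning subjects stay on BAX 855 until PK-tailored dosing begins, and on one reading their OPE opens at screening. The gap of weeks is certain only for naive subjects. This objection stands, and the point is limited accordingly.

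**Regimen comparison.** A reader might also infer that side-by-side AE rates by regimen are not comparable. SAP 8.1 defines the rate over all subjects and names no split by regimen, whereas the exposure, compliance and bleeding sections do name one. Protocol 13.2.4 and SAP 5.11 allow regimen subgroups in general terms, with the detail left to Output Templates that are not among the documents. Such a table is possible but not shown. If one exists, the start-date bias would lie on the PK-tailored side only.

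**Size.** Figures of 20% or more need about half a year of OPE, which fits naive subjects on twice-weekly dosing poorly. They should not be the headline.

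**Constant rate.** During the gap a naive subject has one BAX 855 infusion and otherwise uses another product, so a constant AE rate is an assumption. Restricting the numerator to the OPE would also align the windows, but it would drop AEs soon after first exposure, which is a poor choice for a safety rate.

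**Importance.** The rate is descriptive, with no test or decision rule attached. The inhibitor proportion, AE counts, listings and the rate per 100 infusions are unaffected. That limits the weight of the point but does not remove the mismatch.

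**End date.** OPE stops at the last infusion, while AEs are collected to completion. This applies to both regimens and is small for completers, because the end-of-study visit includes an infusion. It is not part of the sizes given.

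**Conclusion.** The mismatch follows from the SAP's own definitions, and nothing elsewhere in the two documents removes it. For BAX 855 naive PK-tailored subjects, the yearly AE rate omits 5 to 7 weeks of person-time whose AEs are counted. Under a constant AE rate, the subject-level overstatement is about 10-14% at roughly 50 weeks to 1 year of OPE, more with shorter and less with longer follow-up. In the pooled rate it is diluted to about 1% at an affected share of 10% and 6% at 50%; these shares are assumptions. For transitioning and switching subjects, the SAP wording is ambiguous and the gap runs from nil to about 13 weeks. This is a modest upward bias in a descriptive secondary safety rate, worth correcting because the correction is easy.

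**What to change.** - In the SAP, define a safety observation period from the first BAX 855 infusion in this study, whatever its reason, to study completion or discontinuation, less time in the surgery study. Use it as the denominator of the AE rate per year. The surgery deduction fits Protocol 12.1.1.4, which records AEs that start and resolve in that study as medical history.
- Keep OPE for bleeding rates, and state which infusion starts it for transitioning PK-tailored subjects and for those who switch regimen.
- Footnote that, for naive PK-tailored subjects, the new denominator includes some weeks spent mostly on their previous FVIII product.

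The cost is one new definition and one clarification. Infusion, completion and surgery-transfer dates are already collected, so no new data are needed.

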## 8.2 Clinical Laboratory Evaluations

Results from the central laboratory are to be included in the reporting for this study. Results are to be presented using CDISC compliant terms and standard international (SI) units.

Information from the Investigator on abnormal results is to be obtained from the eCRF (*Central Laboratory* eCRF panels).

The following derivations are to be performed based on results obtained from the central laboratory and eCRF:

- A result is considered to be out of range if the observed result is less than the lower limit of the normal range (indicated as "L") or larger than the upper limit of the normal range (indicated as "H"). The normal range is to be provided by the central laboratory.
- A result is to be considered clinically significant if indicated as such by the Investigator on the eCRF.
- Quantitative laboratory measurements reported as "<X", i.e., BLQ, or ">X", i.e., ALQ are to be presented in listings as "<X" or ">X" and summarized in summaries as "0" for "<X" and "X" for ">X".

The following laboratory parameters are to be included in all summaries:

- Hematology:
  - Hemoglobin, hematocrit, red blood cell count including differentials (i.e., basophils, eosinophils, lymphocytes, monocytes and neutrophils), mean corpuscular volume (MCV), mean corpuscular hemoglobin concentration (MCHC) and platelet count.
- Clinical chemistry:
  - o Sodium, potassium, chloride, bicarbonate, total protein, albumin, alanine aminotransferase (ALT), aspartate aminotransferase (AST), total bilirubin, alkaline phosphatase, blood urea nitrogen (BUN), creatinine and glucose.
- Lipid panel:

- Cholesterol, very low density lipoprotein (VLDL), low density lipoprotein (LDL), high density lipoprotein (HDL) and triglycerides.
- Viral serology:
  - o HIV-1Ab, HIV-2Ab, HBcAb, HBsAb, HBsAg and HCVab.

For hematology, clinical chemistry and lipid parameters, summary statistics on observed and change from baseline result and shift tables are to be presented for the SAS. Descriptive statistics on viral serology are to be presented for the SAS.

Descriptive statistics for laboratory results by visit are to be presented in a box-plot for the SAS.

Laboratory results for all parameters (planned or unplanned) are to be listed for the SAS, including separate listings for abnormal and clinically significant results.

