12.7.1 Hematology, Clinical Chemistry and Lipid Panel

Hematology, clinical chemistry and lipid assessments will be performed on EDTA-anticoagulated whole blood and serum, respectively.

The hematology panel will consist of complete blood count [hemoglobin, hematocrit, erythrocytes (ie, red blood cell count), and leukocytes (ie, white blood cell count)] with differential (ie, basophils, eosinophils, lymphocytes, monocytes, neutrophils, as a percentage of total white blood cell count), mean corpuscular volume (MCV), mean corpuscular hemoglobin concentration (MCHC), CD4 counts (at screening only) and platelet counts.

The clinical chemistry panel will consist of sodium, potassium, chloride, bicarbonate, protein, albumin, alanine aminotransferase, aspartate aminotransferase, bilirubin, alkaline phosphatase, blood urea nitrogen, creatinine, and glucose.

The lipid panel will consist of cholesterol, very low density lipoprotein (VLDL), low density lipoprotein (LDL), high density lipoprotein (HDL), and triglycerides.

Details on the sampling of blood for assessment of hematology, clinical chemistry and lipid parameters are presented in Supplement 20.3 and Supplement 20.4.

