20.4 Clinical Laboratory Assessments

20.4.1 Subjects Transitioning from Other BAX 855 Studies on Fixed Dose Prophylactic Treatment Regimen

Assessments ^a	Screening Visit ^b	Follow-Up Visits		End of Study Visit ^d
		6 ± 1 Week Following Screening ^c	Every 3 Months ± 2 Weeks Following Screening ^c	
FVIII pre-infusion ^c	*	P	P	P
FVIII post-infusion ^c	*	P	P	P
TGA pre-infusion (optional)		P	P	P
TGA post-infusion (optional)		P	P	P
VWF antigen (pre-infusion) (optional)		P	P	P
Immunogenicity assays ^f	*	P	P	P
Hematology ^g	*	W	W	W
CD4 count	W		W ^h	
Clinical chemistry ⁱ	*	S	S	S
Lipid panel ⁱ	*	S	S	S
Viral serology ^k	S			

Abbreviations: W = whole blood; P = plasma; S = serum.

^a At all visits subjects must not be actively bleeding and a washout period of at least 84 to preferably 96 hours following the previous dose of BAX 855 should be observed for blood sampling. All laboratory tests will be performed at a central laboratory.

^b The results of the laboratory assessments marked with an asterisk (*) will be obtained/transferred from the end of study visit of the previous BAX 855 study. For subjects transitioning from the surgery study (Study 261204), FVIII assays and lipid panel are not part of the end of study assessments of the surgery study and must be performed at screening.

^c IR determination for FVIII activity, TGA and pre-infusion VWF only if eligibility confirmed.

^d Including cases of withdrawal or discontinuation.

^e FVIII tests are: 1-stage clotting FVIII activity, FVIII chromogenic activity, and FVIII antigen. Samples will be taken within 30 minutes before and 30 ± 15 minutes after infusion of 60 ± 5 IU/kg of BAX 855.

^f Immunogenicity assays are: inhibitory antibodies to FVIII, binding antibodies to FVIII, BAX 855 and PEG, anti-CHO antibodies. For binding antibodies, both IgG and IgM antibodies will be measured.

Continued on Next Page

Continued

- ^g Hematology includes: hemoglobin, hematocrit, red blood cell count, white blood cell count with differential (ie, basophils, eosinophils, lymphocytes, monocytes, and neutrophils), mean corpuscular volume (MCV), mean corpuscular hemoglobin concentration (MCHC), platelet count.
- ^h CD4 count to be tested every 6 months in subjects who are HIV positive.
- ⁱ Clinical chemistry includes: Sodium, potassium, chloride, bicarbonate, total protein, albumin, ALT, AST, total bilirubin, alkaline phosphatase, BUN, creatinine, and glucose.

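### SAP 8.2 attaches the leukocyte differential to the red cell count and does not name the total white cell count among the hematology parameters for summary and shift tables

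*SAP*

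**What the plan says.** **Protocol.** Section 12.7.1 puts "leukocytes (ie, white blood cell count)] with differential" in the complete blood count and expresses the five cell types "as a percentage of total white blood cell count". The hematology footnotes to 20.4.1, 20.4.2 and 20.4.3 give the same panel: "red blood cell count, white blood cell count with differential (ie, basophils, eosinophils, lymphocytes, monocytes, and neutrophils". Changes in clinical laboratory parameters, hematology included, are a secondary safety outcome (8.4.2.2). Section 13.4.4 plans descriptive statistics, shift tables and a summary of clinically significant abnormal values.

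**SAP.** Section 8.2 introduces its parameter list with "The following laboratory parameters are to be included in all summaries". The hematology entry is "Hemoglobin, hematocrit, red blood cell count including differentials (i.e., basophils, eosinophils, lymphocytes, monocytes and neutrophils", followed by MCV, MCHC and platelet count. The outputs are then set: "For hematology, clinical chemistry and lipid parameters, summary statistics on observed and change from baseline result and shift tables are to be presented for the" safety analysis set. A separate sentence covers the plots: "Descriptive statistics for laboratory results by visit are to be presented in a box-plot for the SAS". Results for all parameters, planned or not, go into listings, with separate listings for abnormal and for clinically significant results.

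**The concern.** Basophils, eosinophils, lymphocytes, monocytes and neutrophils are leukocytes, so they cannot form a differential of the red cell count. The SAP item runs two protocol items together and loses the one between them.

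The list is operative text. A programmer who builds the hematology tables from it has an instruction to tabulate the five cell types and none to tabulate the total. The differential does not replace the total if it is reported in percent, because a percentage of the white cell count carries no information on how large that count is. What is at stake is one component of a secondary safety outcome: a shift in total leukocytes across the study population might not be seen in the tables where a safety reader would look for it.

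**Working it through.** The plan states no figure to reproduce here. The check has two parts: a comparison of the lists, and an illustration of what a percentage differential can show.

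**1. List comparison** (protocol 20.4 hematology footnotes against SAP 8.2; CD4 count is left out because the schedule gives it a row of its own)

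| Parameter | Protocol | SAP 8.2 |
|---|---|---|
| Hemoglobin | yes | yes |
| Hematocrit | yes | yes |
| Red cell count | yes | yes |
| White cell count | yes | **no** |
| Five differential cell types | yes, under white cells | yes, under red cells |
| MCV | yes | yes |
| MCHC | yes | yes |
| Platelets | yes | yes |
| Total | 7 + 5 = 12 | 6 + 5 = 11 |

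The SAP adds nothing and drops one parameter. Its chemistry and lipid lists agree with the protocol footnotes item for item.

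**2. Is the omission declared?** SAP 5.7 names two departures from the protocol analysis: imputation of certain missing data, and separate bleeding-rate models by regimen. The white cell count is not mentioned there or in the revision history (SAP 12).

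**3. What a percentage differential shows.** The values are assumed for illustration; the documents give none. Baseline counts (x10^9/L) are neutrophils 3.6, lymphocytes 1.8, monocytes 0.40, eosinophils 0.15 and basophils 0.05, total 6.0. The percentage is 100 x cell type / total.

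| | Total | Neut. % | Lymph. % | Mono. % | Eos. % | Baso. % |
|---|---|---|---|---|---|---|
| Baseline | 6.0 | 60.0 | 30.0 | 6.7 | 2.5 | 0.8 |
| Every type halved | 3.0 | 60.0 | 30.0 | 6.7 | 2.5 | 0.8 |
| Fall of 3.0 in neutrophils only | 3.0 | 20.0 | 60.0 | 13.3 | 5.0 | 1.7 |

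- Proportional fall: neutrophils go from 3.6 to 3.6 / 2 = 1.8, yet the percentage is 100 x 1.8 / 3.0 = 60.0, unchanged. The change from baseline is 0 for all five cell types.
- Fall in one cell type: neutrophils go to 3.6 - 3.0 = 0.6, and 100 x 0.6 / 3.0 = 20.0. The change of -40 percentage points would show in the tables.
- If the differential is tabulated in absolute counts instead, the proportional fall shows too (neutrophils 3.6 to 1.8).

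SAP 8.2 asks for standard international units in general and does not say which form the differential takes.

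**The case against.** A reader might infer that a fall in leukocytes could not appear in any summary, shift table or box-plot. The documents do not support that, for these reasons:

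- The five cell types stay in the list, so a fall concentrated in one of them moves the percentages and shows.
- The SAP gives no unit for the differential. In absolute counts, even a proportional fall would show.
- The box-plot sentence speaks of laboratory results by visit and is not tied to the list.
- The list says what must be included and does not say that nothing else may be. The SAP leaves presentation to Output Templates, which are not among the documents and could contain the count.
- Individual values reach the listings. Under protocol 12.7.8.1 the investigator assesses every abnormal value, and a count judged to be an adverse event enters the tables of SAP 8.1. Protocol 13.4.4 also plans a summary of clinically significant hematology values.

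All of this stands as a limit on the consequence. Two parts carry less weight. SAP 8.2 separates the named parameters, which go into summaries, from all parameters, which go into listings, so the natural working reading is that the named list defines the tables. And for clinically significant values SAP 8.2 provides listings only, so the summary promised in the protocol is not carried into that section.

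It can also be said that this is plainly a dropped phrase. That is very likely right, since the item makes no sense as a red cell parameter. But an evident slip in a specification still has to be corrected before tables are programmed from it.

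**Conclusion.** The specification is wrong as written. SAP 8.2 attaches the differential to the wrong cell line and omits the total white cell count from the parameters named for all summaries, contrary to the protocol and without a declared change. One of 12 hematology parameters is affected.

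The consequence is narrow. The total white cell count is not specified for the observed-value, change-from-baseline and shift tables. On the assumption that the differential is summarised as a percentage, as protocol 12.7.1 expresses it, a roughly proportional change in leukocytes would not show in those tables. Changes confined to one cell type would show, and individual values remain available in the listings. The documents do not establish that the final tables lack the count, nor that the omission was a deliberate analysis choice.

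No primary outcome, estimate or sample size is touched. This is a minor correction worth making.

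**What to change.** In SAP 8.2:

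1. Split the item so that the red cell count stands alone and the white cell count follows as its own parameter with the five cell types attached to it, as in the protocol's "red blood cell count, white blood cell count with differential".
2. Include the white cell count in the summary statistics, change-from-baseline and shift tables, and check that the Output Templates agree.
3. State whether the differential is summarised as a percentage or as an absolute count.

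The cost is one phrase and one sentence in the SAP, and one more parameter in tables that are already planned. The protocol already collects the data, so no new measurement is needed.
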